## **10.1 Adverse Event Characteristics**

**CTCAE term (AE description) and grade:** The descriptions and grading scales found in the revised NCI Common Terminology Criteria for Adverse Events (CTCAE) version 4.0 will be utilized for AE reporting. All appropriate treatment areas should have access to a copy of the CTCAE version 4.0. A copy of the CTCAE version 4.0 can be downloaded from the CTEP web site:

([http://ctep.cancer.gov/protocolDevelopment/electronic\\_applications/ctc.htm](http://ctep.cancer.gov/protocolDevelopment/electronic_applications/ctc.htm))

- a. Identify the grade and severity of the event using the CTCAE version 4.0.
- b. Determine whether the event is expected or unexpected (see Section 10.2).
- c. Determine if the adverse event is related to the study intervention (agent, treatment or procedure) (see Section 10.3).
- d. Determine whether the event must be reported as an expedited report. If yes, determine the timeframe/mechanism (see Section 10.4).
- e. Determine if other reporting is required (see Section 10.5).
- f. Note: All AEs reported via expedited mechanisms must also be reported via the routine data reporting mechanisms defined by the protocol (see Sections 10.6 and 18.0).

NOTE: A severe AE is NOT the same as a serious AE, which is defined in Section 10.4.

## **10.2 Expected vs. Unexpected Events**

*Expected events* - are those described within the Section 15.0 of the protocol, the study specific consent form, package insert (if applicable), and/or the investigator brochure, (if an investigator brochure is not required, otherwise described in the general investigational plan).

*Unexpected adverse events* or suspected adverse reactions are those not listed in Section 15.0 of the protocol, the study specific consent form, package insert (if applicable), or in the investigator brochure (or are not listed at the specificity or severity that has been observed); if an investigator brochure is not required or available, is not consistent with the risk information described in the general investigational plan.

*Unexpected* also refers to adverse events or suspected adverse reactions that are mentioned in the investigator brochure as occurring with a class of drugs but have not been observed with the drug under investigation.

An investigational agent/intervention might exacerbate the expected AEs associated with a commercial agent. Therefore, if an expected AE (for the commercial agent) occurs with a higher degree of severity or specificity, expedited reporting is required.

NOTE: \*The consent form may contain study specific information at the discretion of the Principal Investigator; it is possible that this information may NOT be included in the protocol or the investigator brochure. Refer to protocol or IB for reporting needs.

### 10.3 Attribution to agent(s) or procedure

When assessing whether an adverse event (AE) is related to a medical agent(s) medical or procedure, the following attribution categories are utilized:

- Definite - The AE is *clearly related* to the agent(s)/procedure.
- Probable - The AE is *likely related* to the agent(s)/procedure.
- Possible - The AE *may be related* to the agent(s)/procedure.
- Unlikely - The AE is *doubtfully related* to the agent(s)/procedure.
- Unrelated - The AE is *clearly NOT related* to the agent(s)/procedure.

#### 10.31 AEs Experienced Utilizing Investigational Agents and Commercial Agent(s) on the SAME (Combination) Arm

**NOTE:** When a commercial agent(s) is (are) used on the same treatment arm as the investigational agent/intervention (also, investigational drug, biologic, cellular product, or other investigational therapy under an IND), the **entire combination (arm) is then considered an investigational intervention for reporting.**

- An AE that occurs on a combination study must be assessed in accordance with the guidelines for **investigational** agents/interventions.
- An AE that occurs prior to administration of the investigational agent/intervention must be assessed as specified in the protocol. In general, only Grade 4 and 5 AEs that are unexpected with at least possible attribution to the commercial agent require an expedited report, unless hospitalization is required. Refer to Section 10.4 for specific AE reporting requirements or exceptions.

An investigational agent/intervention might exacerbate the expected AEs associated with a commercial agent. Therefore, if an expected AE (for the commercial agent) occurs with a higher degree of severity or specificity, expedited reporting is required.

- An increased incidence of an expected adverse event (AE) is based on the patients treated for this study at their site. A list of known/expected AEs is reported in the package insert or the literature, including AEs resulting from a drug overdose.
- Commercial agent expedited reports must be submitted to the FDA via MedWatch 3500A for Health Professionals (complete all three pages of the form).

<http://www.fda.gov/downloads/AboutFDA/ReportsManualsForms/Forms/UCM048334.pdf>

#### 10.32 EXPECTED Serious Adverse Events: Protocol Specific Exceptions to Expedited Reporting

For this protocol only, the following Adverse Events/Grades are expected to occur within this population and do not require Expedited Reporting. These events must still be reported via Routine Reporting (see Section 10.6).\*

\*Report any clinically important increase in the rate of a serious suspected adverse reaction (at your study site) over that which is listed in the protocol or investigator brochure as an expedited event.

\*Report an expected event that is greater in severity or specificity than expected as an expedited event.

\*Specific protocol exceptions to expedited reporting should be reported expeditiously by investigators **ONLY** if they exceed the expected grade of the event.

System Organ Class (SOC)	Adverse event/ Symptoms	CTCAE Grade at which the event will not be reported in an expedited manner 
Blood and lymphatic system disorders	Anemia	≤Grade 4
Gastrointestinal	Vomiting	≤Grade 3
	Nausea	≤Grade 3
	Diarrhea	≤Grade 3
General disorders and administrations site conditions	Fatigue	≤Grade 3
Investigations	Lymphocyte count decreased	≤Grade 4
	Neutrophil count decreased	≤Grade 4
	Platelet count decreased	≤Grade 4
	White blood cell count decreased	≤Grade 4

 These exceptions only apply if the adverse event does not result in hospitalization. If the adverse event results in hospitalization, then the standard expedited adverse events reporting requirements must be followed.

The following hospitalizations are not considered to be SAEs because there is no “adverse event” (*i.e.*, there is no untoward medical occurrence) associated with the hospitalization:

- Hospitalizations for respite care
- Planned hospitalizations required by the protocol
- Hospitalization planned before informed consent (where the condition requiring the hospitalization has not changed post study drug administration)
- Hospitalization for elective procedures unrelated to the current disease and/or treatment on this trial
- Hospitalization for administration of study drug or insertion of access for administration of study drug
- Hospitalization for routine maintenance of a device (*e.g.*, battery replacement) that was in place before study entry
- Hospitalization, or other serious outcomes for signs and symptoms of progression of the cancer.

#### 10.4 Expedited Reporting Requirements for IND Agents

##### 10.4.1 Phase 1 and Early Phase 2 Studies: Expedited Reporting Requirements for Adverse Events that Occur on Studies under an IND within 30 Days of the Last Administration of the Investigational Agent/Intervention 

**FDA REPORTING REQUIREMENTS FOR SERIOUS ADVERSE EVENTS (21 CFR Part 312)**

**NOTE:** Investigators **MUST** immediately report to the sponsor **ANY** Serious Adverse Events, whether or not they are considered related to the investigational agent(s)/intervention (21 CFR 312.64)

An adverse event is considered serious if it results in **ANY** of the following outcomes:

- 1) Death
- 2) A life-threatening adverse event
- 3) An adverse event that results in inpatient hospitalization or prolongation of existing hospitalization for  $\geq 24$  hours
- 4) A persistent or significant incapacity or substantial disruption of the ability to conduct normal life functions
- 5) A congenital anomaly/birth defect.
- 6) Important Medical Events (IME) that may not result in death, be life threatening, or require hospitalization may be considered serious when, based upon medical judgment, they may jeopardize the patient or subject and may require medical or surgical intervention to prevent one of the outcomes listed in this definition. (FDA, 21 CFR 312.32; ICH E2A and ICH E6).

**ALL SERIOUS** adverse events that meet the above criteria **MUST** be immediately reported to the sponsor within the timeframes detailed in the table below.

Hospitalization	Grade 1 and Grade 2 Timeframes	Grade 3-5 Timeframes
Resulting in Hospitalization $\geq 24$ hrs	7 Calendar Days	24-Hour 3 Calendar Days
Not resulting in Hospitalization $\geq 24$ hrs	Not required	

**Expedited AE reporting timelines are defined as:**

- "24-Hour; 3 Calendar Days" - The AE must initially be reported within 24 hours of learning of the AE, followed by a complete expedited report within 3 calendar days of the initial 24-hour report.
- "7 Calendar Days" - A complete expedited report on the AE must be submitted within 7 calendar days of learning of the AE.

Serious adverse events that occur more than 30 days after the last administration of investigational agent/intervention and have an attribution of possible, probable, or definite require reporting as follows:

**Expedited 24-hour notification followed by complete report within 3 calendar days for:**

- All Grade 3, 4, and Grade 5 AEs

**Expedited 7 calendar day reports for:**

- Grade 2 AEs resulting in hospitalization or prolongation of hospitalization

 For studies using PET or SPECT IND agents, the AE reporting period is limited to 10 radioactive half-lives, rounded UP to the nearest whole day, after the agent/intervention was last administered. Footnote "1" above applies after this reporting period.

Effective Date: May 5, 2011

#### 10.42 General reporting instructions

The Mayo IND and/or MCCC Compliance will assist the sponsor-investigator in the processing of expedited adverse events and forwarding of suspected unexpected serious adverse reactions (SUSARs) to the FDA and IRB.

Use Mayo Expedited Event Report form

<http://livecycle2.mayo.edu/workspace/?startEndpoint=MC4158-56/Processes/MC4158-56-Process.MC4158-56> and US FDA MedWatch form

<http://www.fda.gov/downloads/AboutFDA/ReportsManualsForms/Forms/UCM048334.pdf> for investigational agents or commercial/investigational agents on the same arm.

**10.43 Reporting of re-occurring SAEs**

ALL SERIOUS adverse events that meet the criteria outlined in table 10.41 MUST be immediately reported to the sponsor within the timeframes detailed in the corresponding table. This reporting includes, but is not limited to SAEs that re-occur again after resolution.

**10.5 Other Required Reporting****10.51 Unanticipated Problems Involving Risks to Subjects or Others (UPIRTSOS)**

Unanticipated Problems Involving Risks to Subjects or Others (UPIRTSOS) in general, include any incident, experience, or outcome that meets **all** of the following criteria:

1. Unexpected (in terms of nature, severity, or frequency) given (a) the research procedures that are described in the protocol-related documents, such as the IRB-approved research protocol and informed consent document; and (b) the characteristics of the subject population being studied;
2. Related or possibly related to participation in the research (in this guidance document, possibly related means there is a reasonable possibility that the incident, experience, or outcome may have been caused by the procedures involved in the research); and
3. Suggests that the research places subjects or others at a greater risk of harm (including physical, psychological, economic, or social harm) than was previously known or recognized.

Some unanticipated problems involve social or economic harm instead of the physical or psychological harm associated with adverse events. In other cases, unanticipated problems place subjects or others at increased *risk* of harm, but no harm occurs.

Note: If there is no language in the protocol indicating that pregnancy is not considered an adverse experience for this trial, and if the consent form does not indicate that subjects should not get pregnant/impregnate others, then any pregnancy in a subject/patient or a male patient's partner (spontaneously reported) which occurs during the study or within 120 days of completing the study should be reported as a UPIRTSO.

**Mayo Clinic Cancer Center (MCCC) Institutions:**

If the event meets the criteria for IRB submission as a Reportable Event/UPIRTSO, provide the appropriate documentation and use the Mayo Clinic Cancer Center Expedited Event Report form <http://livelcycle2.mayo.edu/workspace/?startEndpoint=MC4158-56/Processes/MC4158-56-Process.MC4158-56>, to submit to [[contact]](mailto:[contact]). The Mayo Clinic Compliance Unit will review and process the submission to the Mayo Clinic IRB and work with the IND Coordinator for submission to FDA.

## 10.52 Death

**Note: A death on study requires both routine and expedited reporting regardless of causality, unless as noted below. Attribution to treatment or other cause must be provided.**

Any death occurring within 30 days of the last dose, regardless of attribution to an agent/intervention under an IND requires expedited reporting within 24-hours.

Any death occurring greater than 30 days with an attribution of possible, probable, or definite to an agent/intervention under an IND requires expedited reporting within 24-hours.

**Reportable categories of Death**

- Death attributable to a CTCAE term.
- Death Neonatal: A disorder characterized by cessation of life during the first 28 days of life.
- Death NOS: A cessation of life that cannot be attributed to a CTCAE term associated with Grade 5.
- Sudden death NOS: A sudden (defined as instant or within one hour of the onset of symptoms) or an unobserved cessation of life that cannot be attributed to a CTCAE term associated with Grade 5.
- Death due to progressive disease should be reported as **Grade 5 “Neoplasms benign, malignant and unspecified (including cysts and polyps) – Other (Progressive Disease)”** under the system organ class (SOC) of the same name. Evidence that the death was a manifestation of underlying disease (e.g., radiological changes suggesting tumor growth or progression: clinical deterioration associated with a disease process) should be submitted.

## 10.53 Secondary Malignancy

- A **secondary malignancy** is a cancer caused by treatment for a previous malignancy (e.g., treatment with investigational agent/intervention, radiation or chemotherapy). A secondary malignancy is not considered a metastasis of the initial neoplasm.
- All secondary malignancies that occur following treatment with an agent under an IND will be reported. Three options are available to describe the event:
  - Leukemia secondary to oncology chemotherapy (e.g., Acute Myelocytic Leukemia [AML])
  - Myelodysplastic syndrome (MDS)

- Treatment-related secondary malignancy
- Any malignancy possibly related to cancer treatment (including AML/MDS) should also be reported via the routine reporting mechanisms outlined in each protocol.

#### 10.54 Second Malignancy

A second malignancy is one unrelated to the treatment of a prior malignancy (and is NOT a metastasis from the initial malignancy). Second malignancies require ONLY routine reporting unless otherwise specified.

#### 10.55 Pregnancy, Fetal Death, and Death Neonatal

If a female woman becomes pregnant or suspects that she is pregnant while participating in this study or within 90 days after the last dose, she must inform the investigator immediately and permanently discontinue study drug. The sponsor-investigator must immediately fax a completed Pregnancy Form to the Takeda Department of Pharmacovigilance or designee. The pregnancy must be followed for the final pregnancy outcome.

If a female partner of a male patient becomes pregnant during the male patient's participation in this study, the sponsor-investigator must also immediately fax a completed Pregnancy Form to the Takeda Department of Pharmacovigilance or designee (see Section 8.2). Every effort should be made to follow the pregnancy for the final pregnancy outcome.

Prior to obtaining private information about a pregnant woman and her infant, the investigator must obtain consent from the pregnant woman and the newborn infant's parent or legal guardian before any data collection can occur. A consent form will need to be submitted to the IRB for these patients if a pregnancy occurs. If informed consent is not obtained, no information may be collected.

In cases of fetal death, miscarriage or abortion, the mother is the patient. In cases where the child/fetus experiences an SAE other than fetal death, the child/fetus is the patient.

Suggested Pregnancy Reporting Form:

Pregnancy Report Form (provided by Takeda)

NOTE: When submitting Mayo Expedited Adverse Event Report reports for "Pregnancy", "Pregnancy loss", or "Neonatal loss", the potential risk of exposure of the fetus to the investigational agent(s) or chemotherapy agent(s) should be documented in the "Description of Event" section. Include any available medical documentation. Include this form:

[http://ctep.cancer.gov/protocolDevelopment/electronic\\_applications/docs/PregnancyReportFormUpdated.pdf](http://ctep.cancer.gov/protocolDevelopment/electronic_applications/docs/PregnancyReportFormUpdated.pdf)

#### 10.551 Pregnancy

Pregnancy should be reported in an expedited manner as **Grade 3 "Pregnancy, puerperium and perinatal conditions - Other (pregnancy)"** under the Pregnancy, puerperium and perinatal conditions SOC. Pregnancy should be followed until the outcome is known.

#### 10.552 Fetal Death

Fetal death is defined in CTCAE as "A disorder characterized by death in utero; failure of the product of conception to show evidence of

respiration, heartbeat, or definite movement of a voluntary muscle after expulsion from the uterus, without possibility of resuscitation.”

Any fetal death should be reported expeditiously, as **Grade 4 “Pregnancy, puerperium and perinatal conditions - Other (pregnancy loss)”** under the Pregnancy, puerperium and perinatal conditions SOC.

10.553 Death Neonatal

Neonatal death, defined in CTCAE as “A disorder characterized by cessation of life occurring during the first 28 days of life” that is felt by the investigator to be at least possibly due to the investigational agent/intervention, should be reported expeditiously.

A neonatal death should be reported expeditiously as **Grade 4 “General disorders and administration - Other (neonatal loss)”** under the General disorders and administration SOC.

## 10.6 Required Routine Reporting

### 10.61 Baseline and Adverse Events Evaluations

Pretreatment symptoms/conditions to be graded at baseline and AEs to be graded at each evaluation.

Grading is per CTCAE v4.0 **unless** alternate grading is indicated in the table below:

System Organ Class	Adverse event/Symptoms	Baseline	Each evaluation
Blood and lymphatic system disorders	Anemia	X	X
Gastrointestinal disorders	# of stools	X	
	Diarrhea		X
	Nausea		X
	Vomiting		X
General disorders and administration site conditions	Fatigue	X	X
Investigations	Neutrophil count decreased	X	X
	Platelet count decreased	X	X
Nervous system disorders	Peripheral motor neuropathy	X	X
	Peripheral sensory neuropathy	X	X

10.62 Submit via appropriate MCCC Case Report Forms (i.e., paper or electronic, as applicable) the following AEs experienced by a patient:

- Grade 2 AEs deemed *possibly, probably, or definitely* related to the study treatment or procedure.
- Grade 3 and 4 AEs regardless of attribution to the study treatment or procedure.
- Grade 5 AEs (Deaths)
- Any death within 30 days of the patient’s last study treatment or procedure regardless of attribution to the study treatment or procedure.
- Any death more than 30 days after the patient’s last study treatment or procedure that is felt to be at least possibly treatment related must also be submitted as a Grade 5 AE, with a CTCAE type and attribution assigned.

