### **2.2 Secondary Goals**

- 2.21 To assess the overall response rate (ORR=PR or better) in WM patients treated with ixazomib and ibrutinib.
- 2.22 To assess the time to progression (TTP) in WM patients treated with ixazomib and ibrutinib.
- 2.23 To further characterize the safety and toxicity of the combination of ibrutinib and ixazomib.
- 2.24 To assess the overall survival (OS) in WM patients treated with ixazomib and ibrutinib.

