**Common known potential toxicities, >10%:**

**Cardiovascular:** Peripheral edema, hypertension

**Central nervous system:** Fatigue, dizziness, headache, anxiety, chills

**Dermatologic:** Skin rash, skin infection, pruritis

**Endocrine & metabolic:** Hyperuricemia, hypoalbuminemia, hypokalemia, dehydration

**Gastrointestinal:** Diarrhea, nausea, constipation, abdominal pain, vomiting, decreased appetite, stomatitis, dyspepsia, gastroesophageal reflux disease, upper abdominal pain

**Genitourinary:** Urinary tract infection

**Hematologic & oncologic:** Decreased platelet count, bruise, neutropenia, decreased hemoglobin, petechia, malignant neoplasm (secondary)

**Infection:** infection

**Neuromuscular & skeletal:** Musculoskeletal pain, arthralgia, muscle spasm, weakness, arthropathy

**Ophthalmic:** Dry eye syndrome, increased lacrimation, blurred vision, decreased visual acuity

**Respiratory:** Upper respiratory tract infection, dyspnea, sinusitis, cough, oropharyngeal pain, pneumonia, epistaxis, bronchitis

**Miscellaneous:** Fever

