**Less common known potential toxicities, 1% - 10%:**

**Cardiovascular:** Atrial fibrillation, atrial flutter

**Renal:** Increased serum creatinine

**Limited to important or life threatening:** Abnormal platelet aggregation, hepatic failure, hypersensitivity (includes anaphylactic shock, angioedema, urticaria), interstitial pulmonary disease, onychoclasia, pneumonia due to *Pneumocystis carinii*, pneumonitis, progressive multifocal leukoencephalopathy, renal failure, Stevens-Johnson syndrome, tumor lysis syndrome

15.28 **Drug procurement:** Commercial supplies. Pharmacies or clinics shall obtain supplies from normal commercial supply chain or wholesaler.

15.29 **Nursing Guidelines:**

- There are numerous drug to drug interactions. Record all of patient's medications including OTC, and herbal use. Avoid concomitant use with agents as listed in section 15.16.
- Ibrutinib should be taken with water at approximately the same time each day and can be taken with or without food. Capsules should be swallowed whole.
- Patients should be instructed to avoid eating grapefruit (including juice) and Seville oranges while on ibrutinib.
- Peripheral edema is common. Instruct patients to report this to the study team.
- Gastrointestinal side effects are common (diarrhea, nausea, constipation, abdominal pain, vomiting, etc). Treat symptomatically and monitor for effectiveness of intervention.
- Monitor CBC w/diff. Instruct patients in energy conserving lifestyle (anemia) and to report any unusual bruising or bleeding and/or signs or symptoms of infection to study team.
- Arthralgias, myalgias, and muscle spasm can be seen. Treat symptomatically and monitor for effectiveness.
- Monitor renal function/uric acid levels, especially in patients who may be experiencing dehydration.
- Respiratory symptoms may include, cough, SOB, and URI. Instruct patients to report these symptoms to the study team.
- Rarely patients can experience secondary skin cancers. Instruct patients to report any new skin lesions to the study team.
- Rash can be seen. Instruct patient to report to study team.
- Cardiac arrhythmias have been seen with this agent including a-fib, atrial flutter and ventricular tachyarrhythmia's, some of which have led to death. Instruct patients who experience any palpitations, lightheadedness, syncope, or SOB to see medical care immediately. This is especially important in patients who have pre-existing cardiac issues.

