**16.32 Secondary Outcome Analysis**

16.321 The overall response rate will be estimated by the total number of patients who achieve a CR VGPR, or PR divided by the total number of evaluable patients. All evaluable patients will be used for this analysis. Exact binomial 95% confidence intervals for the true overall response rate will be calculated.

16.322 Time to progression is defined as the time from registration to the earliest date of documentation of disease progression. The distribution of time to progression will be estimated using the method of Kaplan-Meier.

16.323 Overall survival is defined as the time from registration to death due to any cause. The distribution of overall survival will be estimated using the method of Kaplan-Meier.

16.324 AEs: All eligible patients that have initiated treatment will be considered evaluable for assessing AE rate(s). The maximum grade for each type of AE will be recorded for each patient, and frequency tables will be reviewed to determine patterns. Additionally, the relationship of the AE(s) to the study treatment will be taken into consideration.

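### Grade 1-2 counts of several listed ibrutinib harms will be incomplete under 10.61 and 10.62, yet 16.324 tabulates maximum grade for every AE type with no grade floor

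*Combined protocol and SAP*

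**What the plan says.** Section 10.62 governs routine submission: "Submit via appropriate MCCC Case Report Forms (i.e., paper or electronic, as applicable) the following AEs experienced by a patient". Its grade rules are "Grade 2 AEs deemed *possibly, probably, or definitely* related to the study treatment or procedure" and "Grade 3 and 4 AEs regardless of attribution to the study treatment or procedure", followed by deaths. It has no line for Grade 1 or for Grade 2 judged unlikely or unrelated.

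Section 10.61 gives a short table under the instruction "Pretreatment symptoms/conditions to be graded at baseline and AEs to be graded at each evaluation". Nine terms are marked for each evaluation: anemia, diarrhea, nausea, vomiting, fatigue, neutrophil count, platelet count, peripheral motor neuropathy and peripheral sensory neuropathy. Number of stools is recorded at baseline only.

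Section 15.27 lists further ibrutinib toxicities. The cardiovascular line of the band above 10% reads "Peripheral edema, hypertension". The same band contains bruise, petechia, epistaxis, skin rash and infection. The 1%-10% band has "Atrial fibrillation, atrial flutter". None of these is in the 10.61 table.

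The analysis in 16.324 is "The maximum grade for each type of AE will be recorded for each patient, and frequency tables will be reviewed to determine patterns", with relationship to treatment also considered. It states no minimum grade and does not mention that lower grades are collected selectively. The analysis serves secondary goal 2.23: "To further characterize the safety and toxicity of the combination of ibrutinib and ixazomib".

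**The concern.** A maximum-grade table can show only what the form collects. For a term outside 10.61, a patient whose worst event is a non-serious Grade 1, or a non-serious Grade 2 judged unrelated, appears in 16.324 as having had no event. If the nine 10.61 terms are captured at all grades, as 10.61 implies, one table would mix two capture rules. Low-grade neuropathy or fatigue would then not be comparable with low-grade bruising, rash or hypertension.

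This matters for three reasons.

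- Safety of the combination is a stated secondary goal and there is no control arm, so the trial's own frequencies carry the safety description.
- Section 1.3 argues that the two drugs' toxicities do not overlap. Yet rash and peripheral edema are listed as common for both drugs (15.17 and 15.27), and neither is in 10.61.
- The attribution filter on Grade 2 acts when the data are collected. Considering relationship at analysis, as 16.324 proposes, cannot bring back events that were never submitted.

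Baseline has a similar gap. Section 3.29a admits adequately rate-controlled atrial fibrillation and excludes hypertension only if uncontrolled. Section 6.8 requires graded baseline symptoms only for the 10.6 list, which has a row for neither.

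**Working it through.** The plan states no figure on this point, so the check is a comparison of sections followed by an illustration.

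**Step 1: what reaches the form for a term outside 10.61**

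| Worst event | Related | Unlikely or unrelated |
|---|---|---|
| Grade 1, not hospitalized | no line in 10.62 | no line in 10.62 |
| Grade 2, not hospitalized | submitted | no line in 10.62 |
| Grade 1-2, hospitalized 24 h or more | submitted (10.4, 10.1 item f) | submitted (10.4, 10.1 item f) |
| Grade 3-5 | submitted | submitted |

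The third row comes from the expedited table in 10.4, which has a Grade 1-2 column for hospitalization. Item f of 10.1 sends every expedited event to routine reporting as well. The gap is therefore non-hospitalized Grade 1 and non-hospitalized unattributed Grade 2.

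**Step 2: which listed harms fall in the gap**

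| Harm | Listed in 15.27 | Row in 10.61 |
|---|---|---|
| Hypertension | above 10% | none |
| Bruise, petechia, epistaxis | above 10% | none |
| Skin rash | above 10% | none |
| Peripheral edema | above 10% | none |
| Infection | above 10% | none |
| Atrial fibrillation/flutter | 1%-10% | none |

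**Step 3: do the safety rules use anything in the gap?** Section 16.4 counts related first-cycle events of Grade 3 or higher type. Section 16.52 counts related non-hematologic events of Grade 4 or higher. Both lie wholly within what 10.62 collects.

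**Step 4: possible size, under assumptions.** Let T be the true any-grade rate. Let g1 and g2 be the shares of affected patients whose worst grade is 1 or 2, and a the share of those Grade 2 cases attributed to treatment. Ignoring the hospitalization route,

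recorded rate = T × [1 − g1 − g2 × (1 − a)].

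The documents give none of these inputs. Three assumed cases:

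| g1 | g2 | a | Fraction recorded | T = 10% | T = 30% |
|---|---|---|---|---|---|
| 0.2 | 0.4 | 0.9 | 1 − 0.2 − 0.04 = 0.76 | 7.6% | 22.8% |
| 0.4 | 0.4 | 0.8 | 1 − 0.4 − 0.08 = 0.52 | 5.2% | 15.6% |
| 0.6 | 0.3 | 0.5 | 1 − 0.6 − 0.15 = 0.25 | 2.5% | 7.5% |

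With 37 patients and T = 10%, 3.7 affected patients are expected, and 2.8, 1.9 or 0.9 would be recorded. The number 37 is only illustrative: it is the response-evaluable target in 16.22, whereas the AE set in 16.324 is all eligible patients who start treatment. The rate at Grade 3 or higher is T × (1 − g1 − g2) in every case, whether or not the filter applies.

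**The case against.** The case against has real force, and much of it stands.

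- **Other capture routes.** A reader might infer that Grade 1 events are never collected. That holds for the 10.62 list but not for the protocol, because hospitalized Grade 1-2 events of any cause reach the routine data through 10.4 and 10.1 item f. This route is unlikely to pick up ordinary low-grade bruising, rash or edema.
- **Severe events.** A reader might infer that the rates of these harms are understated at every grade, or that the safety rules are weakened. Neither follows. Grade 3-5 events of any cause and related Grade 2 events are collected, and 16.4 and 16.52 depend on nothing else. The individual ibrutinib discontinuation rule for bleeding in 8.3 also concerns grades that 10.62 covers in full.
- **Clinical monitoring.** AE monitoring is scheduled at every visit (4.1), with an EKG prompt for complaints suggesting atrial fibrillation (footnote 6). The limit is on what is submitted, not on what the clinician looks for.
- **The contrast with the nine terms.** Section 10.61 says these terms are graded at each evaluation. Section 10.62 states no exception for them, so all-grade submission is an inference. Form content is left to the Data Submission Schedule (18.1), which is not among the documents. If 10.62 applied to all terms, the contrast would disappear, but low-grade counts would then be incomplete for the nine terms too.
- **Comparison with single-agent rates.** Section 16.324 neither names any-grade incidence nor plans a comparison with the bands in 15.17 and 15.27, and those bands state no grade or attribution basis. Such a comparison is one a reader may make, not one the plan makes.
- **Size.** If nearly all Grade 2 events of known toxicities are called at least possibly related, which 10.3 makes easy, only Grade 1 is materially lost.

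What remains is that 16.324 promises maximum grade for each AE type, while for the omitted harms the lower grades are collected only in part.

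**Conclusion.** The concern holds in a limited form. For atrial fibrillation/flutter, hypertension, bruising/bleeding, rash, peripheral edema and infection, Grade 1-2 and any-grade frequencies would be incomplete and biased downward. They would not be comparable with the 10.61 terms if those are captured at all grades. This weakens secondary goal 2.23 and cannot be repaired at analysis.

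The direction follows from the collection rules. The size does not: the recorded fractions of 25% to 76% rest wholly on assumed grade splits and attribution shares, and no particular shortfall should be cited as a property of the plan. The response decision rule, Grade 3-5 rates, related Grade 2 counts and both safety rules are untouched. The point merits correction because the remedy is cheap, not because any decision in the trial is at risk.

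**What to change.** 1. **Collection (10.61 and 10.62).** Add the six omitted harms to the 10.61 table at baseline and each evaluation, as defined CTCAE terms. Infection and bleeding are classes, so the specific terms need to be named. State in 10.62 that 10.61 terms are submitted at all grades, whatever the attribution. This also gives a graded baseline for conditions allowed at entry.
2. **Analysis (16.324).** Tabulate 10.61 terms at all grades. Tabulate all other terms at Grade 3 or higher (all-cause) and at Grade 2 or higher (at least possibly related). Label any any-grade rate for those other terms as incomplete.

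The first change costs a few more form lines at contacts that already take place, including the telephone contacts that 7.3 allows after cycle 4. It needs no new test or visit. The second is table layout and a footnote, and it can be made alone if the forms can no longer be changed. In that case the tables would be correctly labelled, but the missing low-grade data would stay missing.
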